10.1.2 Secondary Outcomes

Secondary Outcome Title: ^{68}Ga -PSMA-11 PET/CT Sensitivity and Specificity by Participant

Description: The sensitivity and specificity of ^{68}Ga -PSMA-11 PET/CT for detection of tumor by participant will be determined, as confirmed by conventional imaging follow-up and/or histopathology/biopsy, within the following 1 year. The sensitivity and specificity of ^{68}Ga -PSMA-11 PET/CT for detection of tumor lesions is reported with the 95% confidence interval.

Time Frame: 12 months

Secondary Outcome Title: ^{68}Ga -PSMA-11 PET/CT Sensitivity and Specificity by Region

Description: The sensitivity and specificity of ^{68}Ga -PSMA-11 PET/CT for tumor detection by location will be determined, as confirmed by conventional imaging follow-up and/or histopathology/biopsy, within the following 1 year. The regions evaluated will be the prostate bed; pelvis outside of prostate bed including lymph nodes; extrapelvic soft tissue; lymph nodes; and organ metastases (non bone); and bone metastases. The

sensitivity and specificity of ^{68}Ga -PSMA-11 PET/CT for detection at the specified tumor locations is reported with the 95% confidence interval.

Time Frame: 12 months

Secondary Outcome Title: ^{68}Ga -PSMA-11 PET/CT Predictive Value by Participant

Description: The predictive value of ^{68}Ga -PSMA-11 PET/CT for detection of tumor, as confirmed by conventional imaging follow-up and/or histopathology/biopsy, within the following 1 year, is assessed by participant. Positive predictive value (PPV) is the probability that participants identified by ^{68}Ga -PSMA-11 PET/CT as having prostate cancer recurrence, do have prostate cancer recurrence. Negative predictive value (NPV) is the probability that participants not identified by ^{68}Ga -PSMA-11 PET/CT as having prostate cancer recurrence, do not have prostate cancer recurrence. The outcome is reported as the PPV and the NPV of ^{68}Ga -PSMA-11 PET/CT for confirmation of prostate cancer recurrence by participant, with 95% confidence interval.

Time Frame: 12 months

Secondary Outcome Title: ^{68}Ga -PSMA-11 PET/CT Predictive Value by Region

Description: The predictive value of ^{68}Ga -PSMA-11 PET/CT for detection of tumor location, as confirmed by conventional imaging follow-up and/or histopathology/biopsy, within the following 1 year, is assessed by region [prostate bed; pelvis outside of prostate bed including lymph nodes; extrapelvic soft tissue; lymph nodes; and organ metastases (non bone); and bone metastases]. Negative predictive value (NPV) is the probability that participants not identified by ^{68}Ga -PSMA-11 PET/CT as having prostate cancer recurrence, do not have prostate cancer recurrence. The outcome is reported as the PPV and the NPV of ^{68}Ga -PSMA-11 PET/CT for confirmation of prostate cancer recurrence by region, with 95% confidence interval.

Time Frame: 12 months

Secondary Outcome Title: ^{68}Ga -PSMA-11 PET/CT Per-patient Tumor Detection Rates

Description: ^{68}Ga -PSMA-11 PET/CT tumor detection rates by patient, stratified by PSA value in ng/mL (0.2 to < 0.5; 0.5 to < 1.0; 1.0 to < 2.0; 2.0 to < 5.0; \geq 5.0), are reported with mean \pm SD and 95% confidence interval.

Time Frame: 12 months

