INVESTIGATIONAL PRODUCT	⁶⁸ Ga-PSMA-11; also known as: 
 • DFKZ-11 • HBED-CC PSMA • The “Heidelberg compound”
PRIMARY OBJECTIVE	To evaluate ⁶⁸ Ga-PSMA-11 PET/CT for detection of recurrent prostate cancer after initial therapy in patients with elevated PSA
SAMPLE SIZE	200 participants
GOALS	
Prospective single-center, single-arm study.
 
HYPOTHESES
 
 1. At least 30% of these patients will have one or more lesions detected on ⁶⁸Ga-PSMA-11 PET/CT. 2. ⁶⁸Ga-PSMA-11 PET/CT will have sensitivity and specificity of at least 70% in this context. 
STATISTICAL TEST
 
We will calculate point estimates and 95% confidence intervals for:
 
 1. Percentage of patients who had true lesions. 2. Sensitivity and specificity of ⁶⁸Ga-PSMA-11 PET/CT. 
STATISTICAL POWER AND SAMPLE SIZE
 
We expect to recruit 200 patients over the course of this trial. The number of lesions cannot be predicted at this time, however, if our expectation of a 30% discovery rate is correct, the resulting confidence interval would be roughly +/- 7 percentage points, and confidence intervals for specificity/sensitivity would be roughly +/- 10 percentage points.

SCHEMA

Eligible participant with prostate cancer

LIST OF ABBREVIATIONS AND DEFINITION OF TERMS

Ga-68; ^{68}Ga	Gallium-68
IRB	Institutional Review Board
IV	Intravenous
MRI	Magnetic resonance imaging
NPV	Negative predictive value
PPV	Positive predictive value
PET	Positron emission tomography
SUV	Standardized Uptake Value
PSMA	Prostate Specific Membrane Antigen

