7. STUDY CALENDAR

	Pre-Study	Scan Date	24 - 48 Hours Post-Scan	3-12 Months Post-Scan	12 Months (End-of-Study)
Informed consent	X				
Demographics	X				
Medical history	X				
^{68}Ga -PSMA-11		X			
Follow-up Call to Participant			X		
Clinical Follow-up				X	
Data analysis					X

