10.3 Primary Endpoint

The primary endpoint is sensitivity and PPV on a per-patient and per-region-basis (Table 1) of ⁶⁸Ga-PSMA-11 PET for detection of tumor location confirmed by histopathology/biopsy.

Table 1: Region Definition

Region	Description
1	Prostate Bed
2	Pelvis outside of prostate bed including lymph nodes
3	Extrapelvic soft tissue, lymph nodes and organ metastases (non-bone)
4	Bone metastases

10.4 Secondary endpoints:

1. PPV and negative predictive value (NPV) on a per-patient and per-region-basis (Table 1) of ⁶⁸Ga-PSMA-11 PET for detection of tumor location confirmed by histopathology/biopsy and conventional imaging follow-up.
2. Sensitivity and specificity on a per-patient basis of ⁶⁸Ga-PSMA-11 PET for detection of tumor location confirmed by histopathology/biopsy and conventional imaging follow-up.
3. Detection rates on a per-patient basis of ⁶⁸Ga-PSMA-11 PET stratified by PSA value in ng/mL (0.2 to < 0.5; 0.5 to < 1.0; 1.0 to < 2.0; 2.0 to < 5.0; ≥ 5.0).

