11.3.2 Analysis Plan

We will calculate point estimates and 95% confidence intervals for:

1. Percentage of patients who had true lesions.
2. Sensitivity and specificity of ^{68}Ga -PSMA-11 PET/CT.

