11.4 Sample Size

We expect to recruit 200 patients over the course of this trial. The number of lesions cannot be predicted at this time, however, if our expectation of a 30% discovery rate is correct, the resulting confidence interval would be roughly ± 7 percentage points, and confidence intervals for specificity/sensitivity would be roughly ± 10 percentage points.

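### Sensitivity rests on a PET-positive-only population with no scheduled reference test, so false negatives are lost and the estimate is likely biased upward

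*Combined protocol and SAP*

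**What the plan says.** **Reference standard.** Section 10.3 names sensitivity and PPV, per patient and per region, as the primary endpoint of "PET for detection of tumor location confirmed by histopathology/biopsy". Section 10.1.2 scores sensitivity, specificity and predictive values "as confirmed by conventional imaging follow-up and/or histopathology/biopsy, within the following 1 year".

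**Who gets the reference test.** After the scan, the calendar in section 7 lists a telephone call, "Clinical Follow-up" at 3 to 12 months, and data analysis. No biopsy or follow-up imaging appears. Section 2.5, step 12, plans the same clinical follow-up to serve the secondary endpoints, without giving its content. Section 10.1 says that all patients are assessed by region with PET/CT and conventional imaging. It does not say that this is imaging after the scan, and it expects conventional imaging to miss recurrences.

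**Who is analysed.** Section 11.3.1 defines the analysis population as the lesions found by PET/CT. Section 11.3.2 says "We will calculate point estimates and 95% confidence intervals for" the share of patients with true lesions and for sensitivity and specificity. It gives no denominator and no rule for men without a reference result.

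**Target.** Hypothesis 2 in the synopsis is that "PET/CT will have sensitivity and specificity of at least 70% in this context".

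**The concern.** Sensitivity needs a count of recurrences that PET missed. Those can come only from PET-negative men or regions that are in the analysis and have a reference result. The plan secures neither: the stated population leaves such units out, and nothing guarantees that a PET-negative man or region is verified.

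The documents give reason to expect verification to follow the scan. The pilot men in section 2.1 had non-contributory imaging and were observed because no disease could be located. The same section expects better detection to prompt wider nodal surgery or radiation. Section 10.5 lists impact on management as an endpoint. The checklist title describes prior imaging as non-contributory, although this is not an inclusion criterion. PET is then a likely source of biopsy targets.

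At stake is a primary measure under 10.3 and the comparison with the 70% target. A reported sensitivity could reflect who was biopsied more than how well the scan performs.

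**Working it through.** **1. The plan's own figures.** Section 11.4: "We expect to recruit 200 patients over the course of this trial", and "if our expectation of a 30% discovery rate is correct, the resulting confidence interval would be roughly" 7 points either way. Check: 1.96 × √(0.30 × 0.70 / 200) = 0.0635, or 6.4 points; the exact interval is 23.7% to 36.9%. The figure reproduces. The plan adds that "confidence intervals for specificity/sensitivity would be roughly" 10 points either way, without a denominator. At 70% that needs 1.96² × 0.21 / 0.10² = 80.7, so 81 men with (or without) recurrence. The plan does not say where 81 verified men of each kind would come from.

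**2. Population in 11.3.1 taken literally.** Sensitivity = TP / (TP + FN). With PET-found lesions only, FN = 0, so sensitivity = TP / TP = 100%. Likewise TN = 0, so specificity = 0 / (0 + FP) = 0% whenever any lesion is a false positive.

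**3. All scanned men, partial verification.** Let v1 and v0 be the shares of PET-positive and PET-negative men who are verified, with verification depending on the PET result alone.

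- Apparent sensitivity = Se·v1 / (Se·v1 + (1 − Se)·v0)
- Apparent specificity = Sp·v0 / (Sp·v0 + (1 − Sp)·v1)

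True Se = Sp = 70% (the hypothesis 2 threshold). The verification shares are assumptions; the documents give none. The results do not depend on prevalence.

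| v1 / v0 | Apparent sensitivity | Apparent specificity |
|---|---|---|
| 80% / 80% | 0.56/0.80 = 70% | 0.56/0.80 = 70% |
| 80% / 40% | 0.56/0.68 = 82% | 0.28/0.52 = 54% |
| 80% / 20% | 0.56/0.62 = 90% | 0.14/0.38 = 37% |
| 60% / 80% | 0.42/0.66 = 64% | 0.56/0.74 = 76% |

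The true sensitivity that would appear as 70% is 0.7 / (0.7 + 0.3r), where r = v1/v0. It is 0.7/1.3 = 54% at r = 2 and 0.7/1.9 = 37% at r = 4.

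**4. Bounds without any verification shares.** A 30% discovery rate in 200 men gives 60 PET-positive and 140 PET-negative. Assume that all 60 are true positives.

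- No PET-negative man scored as recurrence: 60/60 = 100%.
- All 140 scored as recurrence: 60/200 = 30%.
- The 70% target turns on the 26th such man: 60/85 = 70.6%, 60/86 = 69.8%.

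**5. Can a correction recover the truth?** Begg-Greenes applies the recurrence rate among verified men to all men with the same PET result. Take 80%/40% with an assumed 30% prevalence. Of 84 PET-positive men, 33.6 of 67.2 verified have recurrence, which scales to 42. Of 116 PET-negative men, 7.2 of 46.4 verified have recurrence, which scales to 18. Sensitivity = 42/60 = 70%, the true value. This needs verified PET-negative men: if 5% of 140 are verified, that is 7 men, or 1.4 for each of the five PSA strata in 10.4.

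**The case against.** No section says that the PET result decides who is verified, or that unverified men are excluded. Every participant has planned clinical follow-up (2.5, step 12), and 10.1 speaks of conventional imaging in all patients. Section 11.3.1 may be loose drafting, since 10.3 and 11.3.2 also speak of patients. The bias vanishes with equal verification and reverses if PET-negative men are verified more often, as could happen if men with rising PSA are re-imaged while PET-positive men are treated without biopsy. Histology from extended nodal surgery could also cover PET-negative regions, so 10.3 alone does not force sensitivity to 100%. And sensitivity is primary only under 10.3; the primary outcome in 10.1.1 is a percentage of participants.

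These points make the direction conditional and leave the size unknown. They do not close the gap. Neither 2.5 nor 10.1 guarantees a reference result after the scan, and neither supplies the histology that 10.3 requires. Because 10.1 expects conventional imaging to miss disease, scoring unconfirmed PET-negative men as true negatives would itself raise sensitivity. A reversal is conceivable for imaging but less plausible for biopsy, which needs a target.

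A reader might infer that hypothesis 2 could be met whatever the scanner does. The documents do not support that: the hypothesis also requires specificity of at least 70%, and the mechanism that lifts sensitivity to 82% or 90% lowers specificity to 54% or 37%.

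**Conclusion.** The point holds as a defect in the stated population and reference standard, with a conditional direction of bias. Applied literally, 11.3.1 gives 100% sensitivity however the scan performs, so this is more than missing detail. With the population corrected, upward bias in sensitivity is likely, on the inference that PET-positive men with recurrence are verified more often than PET-negative men with recurrence. The matching fall in specificity assumes that verification depends on the PET result alone.

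The actual size cannot be derived from the documents. Verification ratios of 2 and 4 turn a true 70% into 82% and 90%; those ratios are assumed. The 30% to 100% range uses the plan's own 30% of 200 men and assumes that all 60 PET-positive men are true positives. It would be a mistake to read the plan as stating that verification is PET-driven, or as limiting follow-up to a chance subset; it says neither.

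**What to change.** 1. In 11.3.1, replace the population of PET-found lesions with all scanned participants, and all four regions of Table 1 in each participant, for sensitivity, specificity and NPV.
2. Report the number and share verified, by PET result and by type of reference test.
3. Report sensitivity and specificity with bounds for unverified men. The worst case for both sets unverified PET-negative men to recurrence and unverified PET-positive men to no recurrence; the best case is the opposite.
4. Add a Begg-Greenes or multiple-imputation correction as a sensitivity analysis. Condition on PET result and at most a coarse PSA grouping, use it only where enough PET-negative men are verified, and state its assumptions: verification depends only on the modelled factors, and the reference standard is accurate. The second is doubtful for conventional imaging, given 10.1.
5. In 10.3, rely on PPV, which is already co-primary, as the interpretable histology-based measure among biopsied PET-positive units. Show histology-only sensitivity only with the bounds in item 3.

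The cost is SAP wording and some extra analysis; no scan or biopsy is added. The reported sensitivity is likely to be lower and its uncertainty wider.

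### The by-region predictive-value outcome (10.1.2) carries a participant-level NPV definition, which taken literally gives every region the same NPV and contradicts the outcome's own regional purpose

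*Combined protocol and SAP*

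**What the plan says.** In section 10.1.2, the description of the outcome on predictive value by region makes three statements.

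- Level: the predictive value for tumour location, confirmed "within the following 1 year, is assessed by region", with the regions listed in brackets.
- Definition: "Negative predictive value (NPV) is the probability that participants not identified by" the scan "as having prostate cancer recurrence, do not have prostate cancer recurrence".
- Reporting: "The outcome is reported as the PPV and the NPV of" the scan "for confirmation of prostate cancer recurrence by region, with 95% confidence interval".

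The by-participant outcome just before it contains the same NPV sentence. It also holds the only PPV definition in the documents, which is at participant level: "Positive predictive value (PPV) is the probability that participants identified by" the scan as having recurrence do have it.

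Per-region predictive values are also named as endpoints. Section 10.3 states: "The primary endpoint is sensitivity and PPV on a per-patient and per-region-basis (Table 1) of" the PET scan, against histopathology or biopsy. The first item of 10.4 is "PPV and negative predictive value (NPV) on a per-patient and per-region-basis", against histopathology or biopsy and conventional imaging follow-up. Both point to Table 1, which names four regions. Neither gives a numerator or a denominator.

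**The concern.** A regional NPV should answer this question: when the scan is negative in a region, how often is that region free of tumour? The sentence supplied answers a different one: when the scan finds no recurrence in a man, how often does he have none? The second question has one answer for the whole study.

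Under the literal rule, a man with a positive pelvic node and a negative skeleton never enters the bone NPV, because he has been identified as having recurrence. A PET-negative man whose only recurrence is in the prostate bed would count against the bone NPV. The figure would then say nothing about how the scan performs in bone, pelvis or prostate bed, which is the purpose of the outcome.

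The point reaches beyond one secondary outcome. Per-region PPV is part of the primary endpoint in 10.3, and per-region PPV and NPV are both in 10.4. Those sections depend on a regional counting rule, and the only explicit definition under a by-region heading is the wrong one.

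**Working it through.** The plan states no figure for NPV or PPV, so there is nothing to reproduce. The check is on wording first; a numerical illustration follows.

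**Step 1: the definition.** Let T be a positive scan anywhere in the participant and D recurrence anywhere in the participant. Let T_j and D_j be the same for region j.

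- The sentence in the by-region outcome: NPV = P(D absent | T negative).
- What a by-region outcome needs: NPV_j = P(D_j absent | T_j negative).

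The first expression has no index j. It therefore takes one value for all regions, and that value is the per-participant NPV. This follows from the wording alone.

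**Step 2: whether another section supplies the rule.**

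| Section | What it gives | Regional numerator and denominator? |
|---|---|---|
| 10.1 | Sites evaluated region by region on both kinds of imaging | No |
| 10.3, Table 1 | Four regions; per-region PPV named | No |
| 10.4 | Per-region PPV and NPV named | No |
| 11.3.1 | Analysis population is the PET-identified lesions | No; it contains no PET-negative units, so no NPV can be formed from it |
| 11.3.2 | Estimates and intervals for true lesions, sensitivity and specificity | No; predictive values and regions are not mentioned |

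**Step 3: illustration of size.** All inputs are assumptions: four independent regions, regional sensitivity 0.70, regional specificity 0.95, and prevalences p_j as shown.

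Regional rule: NPV_j = (1 − p_j)(0.95) / [(1 − p_j)(0.95) + p_j(0.30)].

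- p = 0.10: 0.855 / (0.855 + 0.030) = 0.966.
- p = 0.20: 0.760 / (0.760 + 0.060) = 0.927.

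Literal rule: P(disease-free and PET-negative in all four regions) / P(PET-negative in all four regions). With prevalences 10/20/10/10%:

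- Numerator: 0.855³ × 0.760 = 0.4750.
- Denominator: 0.885³ × 0.820 = 0.5684.
- Literal NPV: 0.4750 / 0.5684 = 0.836, the same for every region.

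The same formulas with other prevalences give:

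| Assumed prevalences | Literal NPV, all regions | Region-level NPVs |
|---|---|---|
| 5/15/8/6% | 0.889 | 0.984 / 0.947 / 0.973 / 0.980 |
| 10/20/10/10% | 0.836 | 0.966 / 0.927 / 0.966 / 0.966 |
| 20/30/20/20% | 0.701 | 0.927 / 0.881 / 0.927 / 0.927 |

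With specificity 0.90 instead of 0.95, the literal values become 0.883, 0.828 and 0.688. Under independence the literal value is the product of the four regional NPVs, so it lies below all of them. That ordering depends on the independence assumption; the result of Step 1 does not.

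**The case against.** The strongest reply is that the sentence should not be read apart from its neighbours. The description opens with tumour location assessed by region and closes with reporting by region. Sections 10.3 and 10.4 speak of confirmed tumour location on a per-region basis with reference to Table 1, and 10.1 has sites evaluated by region in all patients. Identical values in every region would make no sense in that context, so an analyst would probably see a sentence carried over by mistake.

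Most of this stands, and it limits what can be claimed:

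- A reader might infer that the trial will report one NPV for all regions. The documents do not support that; the surrounding text points to a regional analysis.
- A reader might infer that a PET-positive node would pass as a true positive when the confirmed tumour is in bone. That is speculative. No matching rule is written, but confirmation is tied to tumour location, which implies matching.
- A reader might count the absent regional PPV sentence as an error in itself. On its own it is only missing detail.

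What the reply does not do is correct the definition. The one explicit rule in the outcome still contradicts the outcome's title and its reporting sentence, and no other section provides the right rule. Intent does not fix a denominator.

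**Conclusion.** Wrong as written. The by-region outcome in 10.1.2 defines NPV at participant level, and that definition yields a single value for all regions, contrary to the outcome's own description. This conclusion rests on the text alone and needs no assumed figure.

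The severity is low. It is a carried-over sentence in an outcome whose intent is clear, not evidence of how the analysis will be run. It still merits correction before analysis, because 10.3 and 10.4 rely on regional counts that are defined nowhere.

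The numerical gap is illustrative only. The documents give no regional prevalence, sensitivity or specificity, and the example also assumes independent regions and complete verification.

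**What to change.** Replace the NPV sentence in the by-region outcome with two definitions tied to the four regions of Table 1. For each region:

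- **NPV** = participants PET-negative in the region and confirmed negative in that same region, divided by participants PET-negative in the region with an evaluable reference standard.
- **PPV** = participants PET-positive in the region with tumour confirmed in that same region, divided by participants PET-positive in the region with an evaluable reference standard.

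For 10.1.2 the reference standard is histopathology/biopsy and/or conventional imaging follow-up within 12 months. Then add the following:

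1. State what makes a region evaluable. Report unverified regions separately and do not count them as negative. Treating every PET-negative region without a confirmed tumour as a true negative would inflate NPV.
2. If regions are pooled, use a 95% confidence interval that allows for clustering within participant.
3. Apply the same counting rule to per-region PPV in 10.3 and to per-region PPV and NPV in 10.4. Section 10.3 keeps its histopathology/biopsy standard.
4. Refer to Table 1 in place of the bracketed list in 10.1.2, whose semicolons can be read as six regions.

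The change is a few sentences and needs no extra patients, scans or procedures. Its cost is precision. If a fraction f of a region's participants is evaluable, interval half-widths grow by about 1/√f for the same observed proportion; for example, f = 0.5 (assumed) gives a factor of 1.41.
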